1. BACKGROUND

Obstructive sleep apnea is the most common of sleep-related disorders and references for the evaluation of this disease often exceeds the sleep clinic's evaluation capacity thus creating important delays in patients' care. In the past two years, the Institut Universitaire de Cardiologie et de Pneumologie de Québec-Université Laval (IUCPQ-UL)'s Department of Respirology has reorganized the clinical activities of its sleep clinic and incorporated the completion of a nocturnal ambulatory investigation before the patients being seen at the sleep clinic. These improvements to the system not only have increased the number of patients seen by the respirologist but also increased the number of time slots available for new patients' consultations. This strategy was victim of its own success as the number of patients evaluated at the sleep clinic increased from 1239 patients per year in 2012-2013 to 2255 patients in 2014-2015. While the number of patients assessed had peaked, the number of references for new patient consultations continues to grow up, with a mean of 83 new references weekly. Our center currently provides between 40 and 55 time slots weekly for patient evaluation by a respirologist, thus creating an excess of requests from 28 to 43 patients per months. Therefore, other strategies must be implemented to preserve accessibility and quality of patients care.

The variety of symptoms presented by patients with sleep-disordered breathing and the complexity, variety and limited access of investigation modalities have led to concentration of investigation and treatment of sleep-related disorders to specialized physicians, mainly composed of respirologists. Two randomized clinical trials (RCT) have demonstrated that these steps can be efficiently performed by properly trained nurses. A recent RCT compared two models of management in the sleep clinic, one with supervision and management by a trained sleep clinic nurse compared to a traditional physician-directed clinical care. Overall the study included 195 patients who were unrepentant snorers with an Epworth Sleepiness Scale (ESS) score greater than 8/24 and an oxygen desaturation index (ODI) (2%) greater than 27 events per hour as determined by home oximetry testing. The prescription of automatic continuous positive pressure (CPAP) treatment or CPAP titration, the interpretation of results and the follow-up were assured independently either by the nurse or the physician. Follow-up at 3 months did not find any difference between the two groups in terms of correction of daytime sleepiness, as measured by the Epworth Sleepiness Scale and by objective measurement by wakefulness test, improvement of quality of life and treatment follow-up.¹ Another RCT evaluated 155 patients randomized to receive primary care management (primary care physician and a community-based nurse trained for the

management of obstructive sleep apnea) or management in a specialized sleep center. Patients enrolled had a high probability of sleep apnea based on symptoms, an ESS greater than 8/24 and ODI (3%) greater than 15 events per hour. Follow up at six months showed no difference between the two groups in terms of improvement in daytime sleepiness measured by the ESS scale, improvement in quality of life and differences in treatment adherence.²

Considering the increasing number of references for evaluation of new patients with clinical suspicion of sleep apnea and the lack of additional resources available from the IUCPQ-UL respirologists, other strategies must be implemented to preserve quality of care. Therefore, this project aims to assess the feasibility and effectiveness of creating a multidisciplinary team at the sleep clinic, allowing a clinical nurse to receive and evaluate selected patients for their first consultation.

2. METHODS

2.1 Study Design Overview

This study is a randomized open label non-inferiority study. The research protocol was approved by the IUCPQ-UL research ethics committee. Patients are to provide written informed consent upon inclusion in the study.

2.2 Settings and Participants

The patients will be selected for inclusion based on information available to the investigators or pulmonologist of the sleep clinic from data from the cardio-respiratory recording reports completed for patients who are to be seen for an initial, non-urgent, outpatient visit to the sleep clinic. The reports are available every morning at the sleep laboratory.

The list of eligible patients will be scheduled by the sleep clinic secretary on the time slots available for consultation. Patients meeting all of the following criteria will be eligible:

- Body mass index (BMI) $\leq 35 \text{ kg/m}^2$;
- Apnea-hypopnea index (AHI) ≥ 20 events per hour according to the report of the cardio-respiratory home recording;
- Central apnea index ≤ 5 events per hour;
- Percentage of recording time spent below 90 % saturation $\leq 15\%$.

Exclusion criteria :

- Patient needing an urgent sleep clinic evaluation
- Patients who had a polysomnographic study required before being seen at the

sleep clinic

- Patients not meeting the aforementioned inclusion criteria

2.3 Randomization

The randomly patient assignation will be in a 1:1 ratio to receive either the evaluation from the nurse or the chest physician. A senior statistician with no clinical involvement in the trial conducted a randomisation list of 200 patients using SAS software v9.4 to generate random numbers. The randomisation allocation was stratified by block of twenty patients to assume an equal number of patients in each group if the study ended much earlier than expected with less patients. After the nurse will have obtained the patient's consent, the nurse will use the list for the patient allocation strategy.

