2.4 Interventions

Multidisciplinary group

Patients randomized in the multidisciplinary group will receive their first sleep clinic evaluation with a specifically trained clinical nurse. For the past five years, a clinical nurse has been attached to the IUCPQ-UL sleep clinic. Her training enables her to complete the follow-up of patients treated with CPAP with a special attention to observance issue, identification and advices regarding any side effects patients may report. Before initiating consultation with patients as needed in this study, a specific training will be performed. Reference documents on diagnostic and therapeutic options will be selected by the respirologist in charge of the sleep clinic and given to the clinical nurse for instructions. She will also have a period of observation in the Ear Nose and Throat clinic and in the sleep laboratory for basic training regarding the completion and scoring of cardio-respiratory recordings by our sleep laboratory technicians. The clinical nurse will then complete her training assisting at the consultations of the respirologist at the sleep clinic's. The minimal duration of this observation period will be 1 month but could be extended if the nurse, the sleep clinic's physician or the principal investigator deemed it necessary.

After completion of the different steps of the training program, the clinical nurse will initially evaluate 2 patients per clinic and progressively increase to 5 patients per clinic. After complete evaluation of the patient, including questionnaire, physical and ENT examination, cardio-respiratory recording analysis and therapeutic discussion with the patient, the patient case will be discussed with the sleep clinic's appointed respirologist to determine the final treatment plan and/or the need for complementary investigations if required. Follow-up will be ensured by the clinical nurse with discussion with the physician if necessary.

Physician directed care group

Patient randomized in the physician directed care group will receive their first sleep clinic evaluation with a respirologist trained in sleep-disordered breathing disorders' evaluation and treatment. The physician will direct the questionnaire and physical examination, perform analysis of the cardio-respiratory recording and determine the treatment plan or additional complementary investigations, if necessary. Follow-up will be ensured by the clinical nurse of the sleep clinic.

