3. FUNDING

The clinical nurse will work part-time on this project over an anticipated period of one year. Taking into account her hourly salary including social security contributions, the budget for this project is 31 860 \$. These fees will be covered by the Sleep Apnea Research and Teaching Fund of the IUCPQ_UL Fondation & Alphonse L'Espérance Funds.

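### A single published block size of 20 leaves about 9% of assignments certain and 62% guessable to the nurse who obtains consent and allocates, even if list entries were hidden

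*Combined protocol and SAP*

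**What the plan says.** Section 2.1 sets the design: "This study is a randomized open label non-inferiority study". Section 2.3 gives the allocation scheme: "The randomly patient assignation will be in a 1:1 ratio", from a list prepared by a statistician without clinical involvement, who "conducted a randomisation list of 200 patients using SAS software v9.4 to generate random numbers". On blocking it says "The randomisation allocation was stratified by block of twenty patients to assume an equal number of patients in each group"; the reason given is balance should the trial stop early. Twenty is the only block size mentioned, and no stratification factor is named. The list is therefore one sequence of ten blocks, each with ten patients per arm.

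On who allocates, section 2.3 says "After the nurse will have obtained the patient's consent, the nurse will use the list for the patient allocation strategy". No envelopes, central service or other concealment step is described.

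Section 2.4 (Interventions) describes the clinic's nurse: "a clinical nurse has been attached to the IUCPQ-UL sleep clinic". She gives the first evaluation in the multidisciplinary arm and follows up its patients. For the physician arm the text says "Follow-up will be ensured by the clinical nurse of the sleep clinic". Section 3 budgets for one nurse: "The clinical nurse will work part-time on this project over an anticipated period of one year".

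**The concern.** In an unblinded trial with one block size and one sequence of blocks, past assignments carry information about the next one. Completed blocks cancel, so a running count shows which arm is behind and more likely to come next. Once one arm has its ten patients, the rest of the block is fixed. Hiding the list entries does not remove this, because the information comes from the blocking rule and from assignments already known.

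Here the person who could hold that count also conducts the consent discussion. If that discussion varied with the expected arm, the two groups could differ in their capacity to improve on the Epworth Sleepiness Scale (ESS). Section 2.2 sets no ESS entry criterion, so patients with very different room for improvement can enter. Section 2.7 plans an ANOVA on changes in score and names no baseline covariate. A shift from selective enrolment would pass into the estimated difference and could favour a non-inferiority claim.

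**Working it through.** The plan gives no figure for predictability, so there is none to reproduce.

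**Inputs.** Block 20, ratio 1:1, list of 200 (section 2.3). Margin 2.0, SD of ESS change 2.0, one-sided alpha 0.025, 100 per group (section 2.7.1). Dropout 10% (section 2.7), leaving 90 per arm.

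**1. Certain assignments.** For a block with m = 10 per arm, the expected number known in advance is 2m/(m+1) = 20/11 = 1.82, or 9.1% of 20. Over ten blocks this is about 18 of 200. The last place is always certain, the last two in 47% of blocks and the last three in 21%.

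**2. Best guess.** Always guessing the arm that is behind gives m + (4^m/C(2m,m) − 1)/2 = 10 + (1048576/184756 − 1)/2 = 12.34 correct of 20. The rate is g = 61.7%, about 123 of 200 against 100 by chance. Simulation agrees. About 27% of assignments can be guessed with probability of at least 2/3.

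**3. Effect if enrolment were steered (assumed).** Suppose patients enrolled when the nurse arm is expected improve by e points more than average, and those enrolled when the physician arm is expected by e points less. Then:

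- Steering at every non-tied count shifts the difference by 2e(2g − 1) = 0.47e.
- Steering only on certain assignments shifts it by 2e × 0.091 = 0.18e.

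The false non-inferiority rate, when nurse-based care is truly worse by the full margin, is Φ(−1.96 + shift/SE). With SD 2.0, SE = 2.0 × √(2/90) = 0.298.

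The SD matters. With the stated inputs, n = 2 × 2.0² × (1.960 + 1.282)²/2.0² = 21.01, so 22 per arm, or 25 after 10% dropout, not 100. An SD near 4.1 gives 89, or 99 after dropout, close to the planned 100. I therefore also show SD 4.1, where SE = 4.1 × √(2/90) = 0.611.

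| Assumed steering | SD | e = 0.25 | e = 0.5 | e = 1.0 |
|---|---|---|---|---|
| None | any | 2.5% | 2.5% | 2.5% |
| Certain assignments only | 2.0 | 3.5% | 4.9% | 8.8% |
| Every non-tied count | 2.0 | 5.8% | 12.0% | 34.8% |
| Every non-tied count | 4.1 | 3.8% | 5.7% | 11.6% |

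**4. Alternative lists (simulated, 200 patients, guesser uses the running count).**

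| Scheme | Correct guesses | Mean absolute imbalance |
|---|---|---|
| Fixed 20 | 61.7% | 1.4 |
| Varied 16/20/24, undisclosed | 61.4% | 1.4 |
| Varied 4/6/8, undisclosed | 68.0% | not computed |
| Fixed 4 | 70.8% | not computed |
| Big stick, limit 10 | about 52% | 4.6 |

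Big stick means a fair coin for each patient unless the arms already differ by 10. Varying the block size removes certainty at block ends but barely lowers the guess rate. Smaller blocks raise it.

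**The case against.** The case against has six parts.

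- **Twenty is a large block.** About 91% of assignments are never certain, and the best strategy errs 38% of the time. This stands. A reader might infer that the nurse can predict assignments generally; the arithmetic supports only partial prediction.
- **Concealment comes first.** Section 2.3 has the nurse use the list and describes no concealment. If she can see upcoming entries, every assignment is known and the block scheme is irrelevant. This stands, so the fix must include hidden entries. Concealment alone is not enough, because assignments become known once made in an open-label trial.
- **Control over who is approached.** A reader might infer that the nurse can pick or defer patients. Section 2.2 gives selection to the investigators or pulmonologist, using numeric criteria, and scheduling to the secretary. Her documented influence is the consent discussion.
- **Identity and knowledge of the nurse.** Section 2.3 does not say that the consenting nurse is the nurse of section 2.4, that she knows the block size, or that she keeps count. The first is a reasonable inference from section 2.4 and the one-nurse budget in section 3. The running-count guess needs only past assignments; certainty also needs the block size, which the protocol prints.
- **Error rates.** The 34.8% figure requires steering at every non-tied count, e = 1.0 (a 2-point gap, one full SD at the plan's value) and SD 2.0. Nothing in the documents supports that combination.
- **Detectability.** Baseline ESS, quality of life and polygraphy are extracted (section 2.6), so imbalance in measured characteristics could be examined, though section 2.7 plans no such check.

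**Conclusion.** The weakness is real but moderate. The design alone determines the 9.1% certain assignments and the 61.7% guess rate. The first assumes a reader who knows the block size and past assignments; the second assumes past assignments only. Both hold even if entries were hidden.

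The effect on the conclusion is conditional. For e from 0.25 to 1.0 the false non-inferiority rate at the margin would be 3.5% to 8.8% if only certain assignments were steered at SD 2.0. If every non-tied count were steered it would be 5.8% to 34.8% at SD 2.0, or 3.8% to 11.6% at SD 4.1. Both e and the extent of steering are assumptions, and e = 0 gives no bias. A reader might infer that the trial's error rate is inflated or that consent will be steered; the documents show neither. They show an avoidable opportunity with no stated safeguard, which is worth correcting before enrolment.

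**What to change.** Before enrolment, amend section 2.3 in three respects:

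1. The same independent statistician regenerates the list with randomly varied block sizes of similar magnitude (for example 16, 20 and 24), not smaller ones.
2. The block sizes are kept in a document that clinic staff do not see and are removed from the protocol text available to them.
3. Each entry is revealed only after consent and enrolment are recorded, for example by sequential opaque envelopes. Without this step the other two achieve nothing.

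This removes the certain assignments for anyone who does not know the sizes. The running-count guess rate stays near 61%.

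Optionally, a big-stick list with limit 10 would lower that rate to about 52%. The price is a mean imbalance of about 4.6 instead of 1.4 and loss of exact balance at every 20 patients, which works against the stated aim of equal groups at an early stop. The loss of precision is small: at 105:95 the variance ratio is (1/95 + 1/105)/(2/100) = 1.0025. Either choice is defensible.

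The cost is one rerun of the SAS list, a set of envelopes or an equivalent release procedure, and a few sentences in section 2.3. No extra patients or visits are needed. Section 2.3 indicates that the list already exists, so the change is simple only if recruitment has not begun.

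### Section 2.3 has the nurse who obtains consent apply the pre-made list of 200, with no step that hides the next assignment, so allocation concealment is not ensured

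*Combined protocol and SAP*

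**What the plan says.** Section 2.1 sets the design: "This study is a randomized open label non-inferiority study". Section 2.3 describes allocation in four steps.

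- Arms and ratio: "The randomly patient assignation will be in a 1:1 ratio to receive either the evaluation from the nurse or the chest physician".
- Generation: a senior statistician with no clinical involvement "conducted a randomisation list of 200 patients using SAS software v9.4".
- Blocking: "The randomisation allocation was stratified by block of twenty patients". The stated reason is to keep the groups equal in size if the trial ends early.
- Use of the list: "After the nurse will have obtained the patient's consent, the nurse will use the list for the patient allocation strategy".

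Section 2.2 covers what happens before consent. On selection it says "The patients will be selected for inclusion based on information available to the investigators or pulmonologist of the sleep clinic", using limits on BMI, AHI, central apnea index and time below 90% saturation. On scheduling it says "The list of eligible patients will be scheduled by the sleep clinic secretary on the time slots available for consultation". Section 2.4 describes the nurse who delivers the multidisciplinary arm: "For the past five years, a clinical nurse has been attached to the IUCPQ-UL sleep clinic". Section 3 also refers to a single clinical nurse. Neither section says whether this is the nurse who takes consent.

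**The concern.** Concealment means that whoever enrols a patient cannot know the next assignment until the patient is irrevocably in the trial. Section 2.3 gives consent and use of the list to the same role and describes no barrier between the two. If the next assignment can be known, the decision to seek consent, and when and how to seek it, can depend on it. Randomisation then no longer guarantees comparable arms.

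Later steps do not undo this. Intention-to-treat analysis (2.7) protects the comparison of patients after randomisation, not the choice of who is randomised next. The primary outcomes are questionnaire scores (ESS and quality of life, 2.5), and the claim is non-inferiority. An imbalance favouring the nurse arm would therefore push towards the conclusion the trial sets out to test.

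**Working it through.** The main check is textual, because the plan gives no figure for this point.

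1. **Is there a concealment step anywhere?** Sections 2.1 to 2.8 and 3 mention no sealed envelopes, no central, telephone or electronic release, no masking of the list, and no third party who holds it. The secretary's role in 2.2 is scheduling only.
2. **Do the stated safeguards fill the gap?** An independent statistician protects how the sequence is generated, but does not hide it from the person enrolling. Consent before allocation fixes when the list is used, not when it can be read. A nurse holding the full list could read ahead and still follow 2.3 to the letter.

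The next check is how much could be known in advance. The inputs, all from 2.3, are 200 assignments, 1:1, in blocks of 20. That gives 200/20 = 10 blocks, each with n = 10 per arm.

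3. **Readable list:** 200 of 200 assignments are knowable.
4. **One-at-a-time release, with block size and all past assignments known** (the open-label design makes past assignments visible):
   - Expected certain assignments per block = 2n/(n+1) = 20/11 = 1.82. Over 10 blocks this is 18.2 of 200, or 9.1%.
   - Expected correct guesses per block, always guessing the arm with more places left = n + (4^n / C(2n,n) − 1)/2 = 10 + (1,048,576/184,756 − 1)/2 = 10 + (5.675 − 1)/2 = 12.34. That is 12.34/20 = 61.7%, against 50% by chance.

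The main exposure is therefore access to the list, not the block size.

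5. **What a bias would do (illustration only).** The SD of 2.0 and margin of 2.0 come from 2.7.1, and 90 per arm is 100 less the 10% dropout in 2.7. The bias values of 0.1 and 0.5 ESS points are assumptions that no figure in the documents informs.
   - SE = 2.0 × √(2/90) = 0.298.
   - One-sided type I error at a true difference of 2.0, with bias b favouring the nurse arm = Φ(b/0.298 − 1.96). This gives 0.025 for b = 0, 0.052 for b = 0.1 and 0.389 for b = 0.5, the last being an extreme case.
   - Power at a true difference of 0 with b = 0.5 against the nurse arm = Φ((2.0 − 0.5)/0.298 − 1.96) = 0.9989.

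Bias would matter for ESS if the truth lay near the margin, and hardly at all if it lay near zero.

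**The case against.** The strongest reply is that this argues from silence. The protocol is very short, the list comes from an independent statistician, and the order is consent first. The wording fits one-at-a-time release as well as an open sheet. That is fair, and it limits the point to what the text does not ensure. It does not remove the point, because 2.3 does state a procedure, and following that procedure would not prevent reading ahead.

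The scope for steering is also narrow. Investigators or the pulmonologist select patients, mostly on numeric limits. The secretary schedules them, and the respirologist shares the treatment decision in the nurse arm. No section gives the nurse discretion to defer an eligible patient. This stands as a limit on likely harm. What remains is whether, when and how consent is sought.

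A reader might infer three stronger things that the documents do not support:

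- *That assignments were seen in advance.* Nothing shows this.
- *That the recruiting nurse is the one whose evaluations are under test.* The shared word in 2.3, and the single clinical nurse in 2.4 and 3, suggest it but do not state it.
- *That the result is biased towards the nurse arm.* Neither size nor direction can be derived. The illustration rests on assumed biases and covers ESS only, although quality of life is also primary.

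**Conclusion.** The concern holds in limited form: the allocation procedure in 2.3 does not ensure concealment, in a trial where blinding offers no second line of defence. Foreknowledge could extend to all 200 assignments if the list is readable. Under one-at-a-time release it would be about 62% correct guesses and about 18 certain assignments, assuming the nurse knows the block size and every past assignment. These figures measure predictability, not bias. An ESS conclusion drawn when the true difference is near zero would be little affected. The gap should be fixed because the remedy is cheap and no later analysis can replace it. The conclusion does not depend on who the recruiting nurse is, although it would weigh more if that nurse also delivers the multidisciplinary arm.

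**What to change.** Replace the last sentence of 2.3 so that the recruiting nurse never holds a readable list, and use one release method only. Two routes from the same list could issue an assignment twice or skip one. Suggested content:

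- The independent statistician keeps the list and prepares 200 sequentially numbered, opaque, sealed envelopes. A locked electronic file that shows one assignment at a time may be used instead, but not as well.
- The next assignment is opened, in order, only after written consent and the enrolment entry (study number, date, time) are recorded.
- The statistician reconciles released assignments with the list and the enrolment log.
- The text states whether the recruiting nurse is the clinical nurse of 2.4.

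The existing list and its block of twenty can stay. Section 2.8 dates enrolment to February to June 2018. If enrolment has already taken place, an amendment cannot conceal past assignments. The sponsor should then report how the list was held and released, and give any lack of concealment as a limitation.

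The cost is one protocol paragraph, minor preparation and a few minutes per patient. Some predictability from the fixed block remains.
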